
Sample Size
 
The primary efficacy analysis will compare the mean telephone administered ALSFRS-R total score change from baseline at Week 36 in the group treated with Acthar to that in the placebo group using mITT analysis population. With 140 mITT subjects in the group treated with Acthar and 70 mITT subjects in the placebo group (210 subjects total), assuming the expected ALSFRS-R total score change from baseline of 6.3 and 9 in Acthar and placebo groups, respectively, the common SD of the ALSFRS-R total score change from baseline at Week 36 of 5.83 (estimated from PRO-ACT database), and dropout rate of 20% prior to Week 36, the study will have at least 80% power to detect the treatment difference at the 0.05 level of significance. Assuming a few subjects might not qualify for the mITT analysis population after randomization, approximately 213 subjects will be enrolled and randomized into Acthar treated group and placebo group in a 2:1 ratio.
 
Efficacy
 
Randomized Treatment Period
 
Summary statistics (n, mean, SD, median, minimum, and maximum) of the baseline value, the value at each scheduled postbaseline evaluation, and the corresponding change from baseline for ALSFRS-R score will be presented by treatment group for all subjects in the mITT population and the Per-Protocol population. ALSFRS-R change from baseline at postbaseline visits will be computed as:
 
Change = baseline value - postbaseline value
 
Baseline is defined as the value observed at randomization (Week 0).
 
The primary efficacy endpoint, change from baseline in the telephone administered ALSFRS-R total score at Week 36 in the Acthar treated group vs the placebo group, will be compared using a mixed model with repeated measures (MMRM) analysis method. ALSFRS-R total score change from baseline will be used as a dependent variable, and the model will include the fixed effects of treatment, visit (categorical covariate), treatment-by-visit interaction, and baseline ALSFRS-R score as continuous covariates. The null hypothesis is that the least squared mean contrast between Acthar and placebo groups at Week 36 equals zero. Significance tests will be based on least-squares means using a two-sided test at $\alpha = 0.05$ (two-sided 95% confidence intervals). An unstructured covariance matrix will be used to model the within-subject variance-covariance. If the unstructured covariance structure matrix results in a lack of convergence, the following tests will be used in sequence: heterogeneous Toeplitz covariance structure, heterogeneous autoregressive covariance structure, and compound symmetry covariance structure. The Kenward-Roger approximation will be used to estimate the denominator degrees of freedom. Least squares mean for each treatment group, least squares mean difference, and 95% confidence intervals between the treatment groups and the corresponding p-value will be reported.
 
All “mean slope decline” type of secondary endpoints will be analyzed using random coefficient model. Change from baseline will be the dependent variable, and treatment time (in month, continuous) and treatment-by-time interaction will be fixed effects and intercept will be random effect. Baseline values will be adjusted. Estimates of slope for each treatment group, estimates of slope difference, 95% confidence interval and the corresponding p-value will be reported.
 
For all “change from baseline” type of secondary [REDACTED] endpoints, the same approach as for the primary efficacy endpoint described above will be used.
 
The primary and secondary endpoints analyses will be performed for the mITT and Per-Protocol populations.
 
[REDACTED]
	

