20.3 Endpoints

20.3.1 Primary Efficacy Endpoint

The primary efficacy endpoint will be the change from baseline in the telephone administered ALSFRS-R total score at Week 36.

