20.5 Efficacy Analysis

20.5.1 Randomized Treatment Period

Summary statistics (n, mean, SD, median, minimum, and maximum) of the baseline value, the value at each scheduled post baseline evaluation, and the corresponding change from baseline for ALSFRS-R score will be presented by treatment group for all subjects in the mITT population and the Per-Protocol population.

ALSFRS-R change from baseline at postbaseline visits will be computed as:

Change = baseline value - postbaseline value

Baseline is defined as the value observed at randomization (Week 0).

The primary efficacy endpoint, change from baseline in the telephone administered ALSFRS-R total score at Week 36 in the Acthar treated group vs the placebo group, will be compared using a mixed model with repeated measures (MMRM) analysis method. ALSFRS-R total score change from baseline will be used as a dependent variable, and the model will include the fixed effects of treatment, visit (categorical covariate), treatment-by-visit interaction, and baseline ALSFRS-R score as continuous covariates. The null hypothesis is that the least squared mean contrast between Acthar and placebo groups at Week 36 equals zero. Significance tests will be based on least-squares means using a two-sided test at $\alpha = 0.05$ (two-sided 95% confidence intervals). An unstructured covariance matrix will be used to model the within-subject variance-covariance. If the unstructured covariance structure matrix results in a lack of convergence, the following tests will be used in sequence: heterogeneous Toeplitz covariance structure, heterogeneous autoregressive covariance structure, and compound symmetry covariance structure. The Kenward-Roger approximation will be used to estimate the denominator degrees of freedom. Least squares mean for each treatment group,

least squares mean difference, and 95% confidence intervals between the treatment groups and the corresponding p-value will be reported.

All “mean slope decline” type of secondary endpoints will be analyzed using random coefficient model. Change from baseline will be the dependent variable, and treatment time (in month, continuous) and treatment-by-time interaction will be fixed effects and intercept will be random effect. Baseline values will be adjusted. Estimates of slope for each treatment group, estimates of slope difference, 95% confidence interval and the corresponding p-value will be reported.

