20.10 Statistical Power and Sample Size Considerations

The primary efficacy analysis will compare the mean telephone administered ALSFRS-R total score change from baseline at Week 36 in the group treated with Acthar to that in the placebo group using mITT analysis population. With 140 mITT subjects in the group treated with Acthar and 70 mITT subjects in the placebo group (210 subjects total), assuming the expected ALSFRS-R total score change from baseline of 6.3 and 9 in Acthar and placebo groups, respectively, the common SD of the ALSFRS-R total score change from baseline at Week 36 of 5.83 (estimated from PRO-ACT database), and dropout rate of 20% prior to Week 36, the study will have at least 80% power to detect the treatment difference at the 0.05 level of significance. Assuming a few subjects might not qualify for the mITT analysis population after randomization, approximately 213 subjects will be enrolled and randomized into Acthar treated group and placebo group in a 2:1 ratio.

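### If the three preceding covariance structures all fail to converge, the primary MMRM falls back to compound symmetry with model-based standard errors, which understate the Week 36 standard error (minor)

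*Combined protocol and SAP*

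**What the plan says.** The primary endpoint (section 20.3.1) is the "change from baseline in the telephone administered ALSFRS-R total score at Week 36". Section 20.5.1 analyses it with an MMRM containing treatment, visit as a category, their interaction and the baseline score. The null hypothesis is a zero contrast between arms at Week 36, tested two-sided at 0.05.

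The unstructured matrix is fitted first. If it does not converge, section 20.5.1 moves to heterogeneous Toeplitz and then to "heterogeneous autoregressive covariance structure, and compound symmetry covariance structure"; the synopsis gives the same list, "heterogeneous Toeplitz covariance structure, heterogeneous autoregressive covariance structure, and compound symmetry covariance structure". Kenward-Roger supplies the denominator degrees of freedom. Neither place names an empirical (sandwich) standard error for any step.

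Section 20.5.1 applies the same approach to the secondary endpoints of the change-from-baseline type, and repeats the analyses in the Per-Protocol population. Sections 20.1 and 20.5.2 leave further detail to a separate SAP, which is not part of the document reviewed here.

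**The concern.** Subjects with ALS decline at different rates. The protocol relies on this itself when it stratifies on predicted decline of at most versus more than 1 point per month (section 15.1.1). If slopes differ, the variance of change from baseline is small at Week 4 and largest at Week 36. Compound symmetry averages those variances, so the standard error at Week 36, the one visit that decides the trial, is built on too small a variance. Kenward-Roger does not repair this, because it takes the fitted structure as correct.

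The rule would be applied mechanically if reached. The primary p-value and confidence interval would then be anti-conservative. The two fallbacks before it give Week 36 its own variance and do not share this averaging problem.

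**Working it through.** **Inputs from the protocol.** Section 20.10: 140 and 70 mITT subjects, "expected ALSFRS-R total score change from baseline of 6.3 and 9 in Acthar and placebo groups, respectively", SD 5.83 at Week 36, 20% dropout. Sections 14.3 to 14.5: nine post-baseline visits, Weeks 4, 8, …, 36.

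**Assumed, because the protocol gives no variance before Week 36.** The variance pattern over visits (random slopes, random walk, or half of each); visit-noise SD e from 1 to 3 points; baseline SD 5.5; the dropout pattern.

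**1. The plan's own figure.** With 20% dropout, 112 and 56 subjects remain.
- SE = 5.83 × √(1/112 + 1/56) = 0.954.
- 2.7/0.954 = 2.83, and Φ(2.83 − 1.96) = 80.8%.

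This agrees with "the study will have at least 80% power to detect the treatment difference at the 0.05 level of significance", so the inputs are being read as the plan intends.

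**2. Closed form, complete data.** The estimate is the Week 36 difference in means. Compound symmetry gives it the mean visit variance V̄ in place of the Week 36 variance V₃₆ = 5.83² = 33.99. Hence

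type I error = 2 × [1 − Φ(1.96 × √(V̄/V₃₆))].

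With random slopes, and t scaled to 1 at Week 36, V(t) = s²t² + 2e² and s² = 33.99 − 2e². Over the nine visits the mean of t² is 285/729 = 0.391, so V̄ = 0.391s² + 2e².

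| e | s² | V̄ | V₃₆/V̄ | SE understated by a factor of | Type I error |
|---|---|---|---|---|---|
| 1 | 31.99 | 14.51 | 2.34 | 1.53 | 20.0% |
| 1.5 | 29.49 | 16.03 | 2.12 | 1.46 | 17.8% |
| 2 | 25.99 | 18.16 | 1.87 | 1.37 | 15.2% |
| 2.5 | 21.49 | 20.90 | 1.63 | 1.28 | 12.4% |
| 3 | 15.99 | 24.25 | 1.40 | 1.18 | 9.8% |

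Limiting cases: slopes with no noise give 22.0%; variance growing linearly with time gives 14.4%; equal variance at every visit gives 5.0%.

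**3. Simulation of the protocol's model under the null.** REML compound-symmetry fit, 140 versus 70 subjects, nine visits, t reference on 200 df (close to Kenward-Roger at this size). There were 3 variance patterns × 5 noise SDs × 3 dropout patterns (none; 20% at random; 11–16% depending on the last score) = 45 scenarios of 1,500 trials each.

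| Variance pattern | Type I error, model-based SE |
|---|---|
| Random slopes | 9.9% to 21.7% |
| Half slopes, half random walk | 9.1% to 18.1% |
| Random walk | 8.3% to 16.2% |

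A mid-range case (random slopes, e = 2, 20% dropout at random): model SE 0.63 against a true SE of 0.90, type I error 17.1%.

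**4. Same fits with a sandwich SE.** Type I error was 4.3% to 6.5% over all 45 scenarios. Monte Carlo error is about √(0.05 × 0.95/1,500) = 0.6 points per scenario.

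**5. How likely is the step to be reached?** The unstructured matrix has 9 × 10/2 = 45 parameters for 210 subjects. A separate simulation (Week 36 SD 5.83, noise SD 1, 2 or 3, 20% dropout, 0% or 5% intermittent missingness) fitted it by REML, and it converged in 360 of 360 trials. The rule of three bounds the failure rate at about 3/360 = 0.8%. If every such failure went straight to compound symmetry at 22% error, the overall rate would be 0.0083 × 22% + 0.9917 × 5% = 5.1%. Two more structures would also have to fail, so the effect should be smaller still.

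**The case against.** The strongest reply is that compound symmetry will almost certainly not be used. That stands, and it sets the priority. A reader might infer from the 8% to 22% range that the primary test runs at that error rate. The protocol does not support this: the unstructured matrix comes first, two heterogeneous-variance structures follow, and step 5 puts the effect on overall error at about 0.1 percentage point or less. Step 5 used one optimiser on Gaussian data, not the trial's software on real scores, so it shows that failure is improbable and not that it is impossible.

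Second, the size rests on assumed variances before Week 36. This also stands, which is why a range is given. The direction needs only that the Week 36 variance exceeds the average over visits.

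Third, the separate SAP may already specify the standard error. It may, but the protocol names this sequence in two places, and an unseen document cannot be assumed to change it.

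Fourth, a reader might conclude that compound symmetry should simply be deleted. That would leave no stated rule if both heterogeneous structures also failed, so the plan would be less fully prespecified than it is now.

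**Conclusion.** This is a real but conditional defect of minor priority. If the primary analysis reaches compound symmetry as written, the Week 36 p-value and confidence interval are anti-conservative, with two-sided type I error of about 8% to 22% in the cases simulated. The range assumes Week 36 SD 5.83, variance that grows by random slopes, a random walk or a mix, and visit-noise SD of 1 to 3. It is a statement about one fallback step and not about the trial's expected error rate, which stays close to 5%. Nothing here counts against the unstructured analysis or the two intermediate fallbacks.

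**What to change.** Keep the sequence in section 20.5.1 and the synopsis. Add that, at the compound-symmetry step, the Week 36 contrast is tested with empirical (sandwich) standard errors, using a degrees-of-freedom rule compatible with them, for example between-within. State that this replaces Kenward-Roger at that step only, because Kenward-Roger adjusts the model-based covariance and does not carry over to the sandwich estimator. Optionally, require a retry of the unstructured fit with other starting values or algorithm settings before leaving it. Carry the same wording into the separate SAP.

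The cost is wording only, with no effect on conduct, data collection or sample size. Sandwich standard errors are slightly more variable, which matters little with about 210 subjects. They correct the standard error and not the point estimate. The simulations used the null hypothesis throughout, so they do not test whether compound symmetry biases the estimate when dropout depends on earlier scores and the arms differ.

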15.1 Methods of Assigning Subjects to Treatment Groups

15.1.1 Randomization and Stratification

Subjects will be randomized according to a computer-generated allocation scheme to receive either Acthar 0.2 mL (16 U) or placebo 0.2 mL. Both investigators and the subjects will be blinded to the treatment assignment. The randomization will be stratified for riluzole use (yes/no) and the predicted values of the 9-month decline rate of ALSFRS score from baseline (≤ 1 point change/month vs > 1 point change/month) generated from the prize winning algorithm of the DREAM Phil Bowen ALS Prediction Prize4Life Challenge ([Küffner et al, 2015](#)).

In the Randomized Treatment Period, for each stratum, a separate randomization scheme will be produced. A block randomization will be performed. Subjects will not be randomized in the Open Label Extension Period. The biostatistician will decide on the details at the time of the creation of the randomization scheme.

The DREAM Phil Bowen ALS Prize4Life Challenge was issued to promulgate development of algorithms that could predict disease progression in ALS. The algorithm developers were provided with a small subset of data from the PRO-ACT database that included 3 months of individual patient level clinical trial information that was to be used to predict disease progression over the subsequent 9 months. There were 37 algorithm submissions, and each algorithm was then evaluated on a separate data set from the PRO-ACT database. The 2 winning algorithms both predicted disease progression better than a baseline model and clinicians using the same data.

Mallinckrodt contacted the developers of 1 of the prize winning algorithms in order to apply the algorithm to stratify the subjects in a previous trial (QSC01-ALS-01, [Mallinckrodt, 2016a](#)). The algorithm was modified to only use the available variables as predictors, which were collected from subjects' Screening Visit. The algorithm was validated with a subset of PRO-ACT data, and the root mean square error of the validation is 0.517, which is very close to the original algorithm. In this study, the ALSFRS-R score collected at the Baseline Visit will be converted to ALSFRS score by dropping the last 2 questions (Questions 11 and 12) since most of the records in PRO-ACT database use ALSFRS scoring system.

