20 STATISTICAL METHODS AND PLANNED ANALYSIS

20.1 General Considerations

This section provides a general description of the statistical methods to be used in analyzing both safety and efficacy data. The key statistical issues or considerations will be addressed. A more detailed statistical analysis plan will be provided in a separate document that will be finalized prior to interim analysis.

Unless otherwise specified, all statistical tests will be two-sided with a significance level of 0.05. Summary statistics will be provided for all study variables with descriptive statistics (number of observations, mean, standard deviation, median, minimum, and maximum) for numerical (or continuous) variables. Frequency and percentages will be calculated for categorical variables. Data summary and analyses will be performed with SAS 9.2 or higher.

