20.3.2 Secondary Efficacy Endpoints- Randomized Treatment Period

[figure not shown]
- Mean slope of the telephone administered ALSFRS-R total score decline from baseline in the group treated with Acthar vs the placebo group.
- Mean slope of investigator administered ALSFRS-R total score decline from baseline in the group treated with Acthar vs the placebo group.
- Change from baseline in telephone administered ALSFRS-R total score and investigator administered ALSFRS-R total score over time.
- Mean slope of pulmonary function tests (FVC and FEV1) decline from baseline in the group treated with Acthar vs the placebo group.

[figure not shown]

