For all “change from baseline” type of secondary endpoints, the same approach as for the primary efficacy endpoint described above will be used.

The primary and secondary endpoints analyses will be performed for the mITT and Per-Protocol populations.

[REDACTED]

[REDACTED]

[REDACTED]

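### The slope model is labelled random coefficient but makes only the intercept random; run as written, its slope-difference standard error is too small

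*Combined protocol and SAP*

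**What the plan says.** Section 20.5.1 states that every slope-decline "type of secondary endpoints will be analyzed using random coefficient model". The next sentence gives the terms: "treatment time (in month, continuous) and treatment-by-time interaction will be fixed effects and intercept will be random effect". The Synopsis repeats it: "treatment-by-time interaction will be fixed effects and intercept will be random effect". Section 20.5.1 asks for a slope estimate per arm, the slope difference, a 95% confidence interval and a p-value.

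Section 20.3.2 lists slope endpoints for the telephone ALSFRS-R, for the investigator ALSFRS-R ("Mean slope of investigator administered ALSFRS-R total score decline from baseline in the group treated with Acthar vs the placebo group"), and for FVC and FEV1.

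The unstructured covariance, its fall-back structures and Kenward-Roger all belong to the paragraph on the primary MMRM. The clause that "the same approach as for the primary efficacy endpoint described above will be used" covers only secondary endpoints of the change-from-baseline type, so it does not reach the slope endpoints. No residual covariance and no robust variance is named for the slope model. Section 20.1 promises a more detailed SAP, to be "finalized prior to interim analysis"; it is not among the documents available here.

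**The concern.** A model whose only random effect is the intercept lets subjects differ in level but not in rate of decline. With independent residuals it also forces the variance of change to be the same at Week 4 as at Week 36, which is implausible in a progressive disease.

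The protocol expects subjects to differ in rate. Section 15.1.1 stratifies randomization on "the predicted values of the 9-month decline rate of ALSFRS score from baseline", split at 1 point per month. It also reports a root mean square error of 0.517 for that prediction; the unit is not stated, but if it is points per month, a good deal of spread remains after prediction. Section 20.10 plans on "the common SD of the ALSFRS-R total score change from baseline at Week 36 of 5.83".

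If slopes differ and the model does not allow for it, each subject's visits are counted as nearly independent information on the slope. The confidence interval is then too narrow and the test rejects a true null too often. A nominally significant slope for an inactive drug could stand beside a null MMRM of the same telephone ALSFRS-R data.

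**Working it through.** **The plan's own figure.** The protocol states no power or standard error for the slope endpoints. Its primary power claim reproduces: 140 and 70 less 20% leave 112 and 56. SE = 5.83 × √(1/112 + 1/56) = 0.954, and 2.7/0.954 − 1.96 = 0.87, which gives power of about 81% against the stated minimum of 80%. The SD of 5.83 is therefore used below as the protocol uses it.

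**Inputs from the documents.**
- Arms of 140 and 70, 20% dropout, SD of Week 36 change 5.83 (section 20.10).
- Telephone ALSFRS-R at 9 postbaseline visits, every 4 weeks; investigator ALSFRS-R at 3, Weeks 12, 24 and 36 (Table 7-1).
- Two-sided 5% tests (section 20.1).

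**Assumptions.**
- Visit-error SD e of 1, 2 or 3 points, independent between visits and also present at baseline.
- Linear decline within each subject.
- The same SD of 5.83 for the investigator scale.

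**Implied spread of slopes.** Week 36 is 8.28 months. Change at Week 36 carries two visit errors plus the slope contribution, so s² = (5.83² − 2e²)/8.28². This gives s = 0.68, 0.62 and 0.48 points per month.

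**Closed form, complete data, m visits.** Sxx is the sum of squared deviations of the visit times in months: 50.8 for the telephone schedule and 15.2 for the investigator schedule.
- True variance of one subject's slope: e²/Sxx + s².
- Variance implied by the random-intercept model: e²/Sxx + s²/(m − 1), because slope variation is absorbed into the residual and spread over m − 1 degrees of freedom per subject.
- Type I error: 2 × [1 − Φ(1.96/ratio)], where ratio is true SE over reported SE.

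For example, telephone with e = 1: true 1/50.8 + 0.467 = 0.486; reported 1/50.8 + 0.467/8 = 0.078; ratio √(0.486/0.078) = 2.50; type I error 43%.

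| Endpoint | e | SE ratio | Type I, closed form | Type I, simulation A | Type I, simulation B | Random slope fitted (B) |
|---|---|---|---|---|---|---|
| Telephone | 1 | 2.50 | 43.2% | 44.0% | 40.7% | 4.9% |
| Telephone | 2 | 1.91 | 30.4% | 30.9% | 31.3% | 5.5% |
| Telephone | 3 | 1.41 | 16.5% | 18.3% | 16.8% | 6.0% |
| Investigator | 1 | 1.33 | 14.2% | 15.6% | 15.2% | 4.9% |
| Investigator | 2 | 1.19 | 10.0% | 10.7% | 11.5% | 4.2% |
| Investigator | 3 | 1.08 | 6.9% | 7.5% | 7.9% | 5.3% |

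Both simulations used REML, 140:70 and 20% dropout, with no treatment effect. A ran 1,500 trials per setting without the baseline covariate; B ran 1,000 with it. Leaving the covariate out therefore does not create the result. Coverage of the nominal 95% interval is one minus the type I error: 56%, 69% and 82% for the telephone scale in A, and 84%, 89% and 93% for the investigator scale.

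**Checks on the cause (simulation B, telephone, e = 2).** With a slope SD of only 0.30, below the implied range, type I error is still 14.7%. With no slope variation, the reported SE is 0.98 of the empirical SD and type I error is 6.5% (Monte Carlo SE about 0.7 points; the random-slope fit gives 5.9% on the same setting). The distortion thus comes from between-subject slopes.

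**The case against.** The strongest reply is that the sentence is incomplete rather than wrong. It names no residual covariance, so the figures above describe one way of completing it. Keeping the random intercept but giving the residuals an AR(1) structure, the same large-sample calculation puts type I error at about 12% to 15% for the telephone scale and about 12%, 6% and 5% for the investigator scale. An unstructured residual would remove the distortion. This stands as a limit on the size. It does not rescue the text: independent residuals are what a programmer gets by default, and the telephone test is still oversized under AR(1).

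Second, a random coefficient model normally includes a random slope, the sentence is loosely drafted, and the SAP may supply one. That may well be the intention. But the intercept-only rule is stated in two places, and an SAP that changed it silently would conflict with the protocol.

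Third, the magnitudes rest on an assumed visit error, on strictly linear decline, and on applying the telephone SD to the investigator scale. That is fair; at the low end, the investigator figure is close to nominal.

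Fourth, the endpoints are secondary and unranked in a Phase 2b study, and a slope can differ from the Week 36 contrast for legitimate reasons, since it uses all visits. Both are true. They limit the consequence but do not make the interval correct.

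**Conclusion.** The concern holds. As written, the slope model leaves out the between-subject variation in decline that the protocol itself expects, and its confidence intervals and p-values would be too optimistic. With independent residuals and a visit-error SD of 1 to 3 points, the nominal 5% test rejects a true null in roughly 16% to 44% of trials for the telephone ALSFRS-R and 7% to 16% for the investigator ALSFRS-R. The direction needs only that slopes differ between subjects; the exact size depends on the assumed visit error and residual structure. FVC and FEV1 slopes share the mechanism, but the documents give no SD for them, so no figure can be derived. The primary MMRM and its power are untouched. This should be fixed, but it does not threaten the primary analysis.

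**What to change.** In section 20.5.1 and the Synopsis, replace the clause that makes only the intercept random. State that subject-specific intercept and slope on time are random effects with an unstructured 2x2 covariance matrix and independent residuals. State Kenward-Roger degrees of freedom for this model too, since the text gives them only for the MMRM. It is worth adding a convergence fall-back that keeps the random slope, as the MMRM paragraph already has a fall-back sequence. Carry the same wording into the SAP before it is finalized ahead of the interim analysis.

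The cost is one sentence in two places, its repeat in the SAP, and one RANDOM statement in SAS. No new data are needed. Intervals become wider: in simulation B the mean reported SE of the slope difference rises from 0.043–0.072 to 0.100–0.105 points per month for the telephone scale, and from 0.086–0.133 to 0.111–0.145 for the investigator scale. That width reflects the real uncertainty.
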